#### 4.4 Unscheduled Data

Except for ACTH stimulation test results as described below, data obtained from unscheduled assessments (which also includes early exit visits) will only be considered for baseline determination; otherwise, unscheduled data will not be used in summary tables or included in the analyses. All unscheduled data will be presented in the listings.

ACTH stimulation test results will be mapped via the windowing rules in the below table. When more than one result for a subject occurs within one visit window, the worst result (i.e., Fail) will be mapped to that visit.

Visit (Mapped)	Target Day	Study Day Range
Screening		<1
Week 1	Day 3	1-9
Week 2	Day 15	10-22
Week 4	Day 29	23-43
Week 8	Day 57	44-71
Week 12	Day 85	72-106
Week 18	Day 127	107-148
Week 24	Day 169	149+

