### **3.8.4.2 Clinical Laboratory Assessments**

Clinical laboratory assessments will be summarized using standard summary statistics for continuous parameters and using frequencies and percentages for categorial parameters. Results will be listed for each subject and flagged high or low relative to the normal range where appropriate. Clinical laboratory test results will be listed in SI units (Metric). Concentration values below the limit of quantification (BLQ) will be analyzed at the lower limit of quantification (LLOQ) when calculating summary statistics.

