#### Clinical Chemistry and Hematology

Clinical chemistry and hematology values will be presented at Screening, Baseline, Week 1, Week 2, Week 4, Week 12 and Week 24 (End of Study) or Early Termination. HbA1c will be presented at Screening and at Week 24 (End of Study) or Early Termination visit.

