#### Serum Cortisol

Serum cortisol will be presented at Screening, Baseline, Week 1, Week 2, Week 4, Week 8, Week 12, Week 18, and Week 24 (End of Study) or Early Termination.

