### **3.8.4.3 Vital Signs**

	EP-104IAR-201 Statistical Analysis Plan	Version: Final 1.0
	Date: 14-Jun-2023	Page 27 of 38

Vital sign measurements will be summarized at Screening, Baseline and 1-hour post-dose, Week 2, Week 4, Week 8, Week 12, Week 18, and Week 24 (End of Study) or Early Termination. Vital signs include systolic and diastolic blood pressure (SBP and DBP), heart rate (HR), respiration rate (RR) and body temperature. Weight will also be summarized per its collection schedule at Screening, Baseline, Week 12, and Week 24 (End of Study) or Early Termination. Vital signs will be summarized as absolute values and change from baseline using standard summary statistics.

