#### **3.8.4.4 Physical Examination**

Physical examinations will be presented at Screening, Baseline, Week 12, and Week 24 (End of Study) or Early Termination. Physical examinations include assessments of general appearance, skin, HEENT (head, ears, eyes, nose and throat), chest and lungs, cardiovascular, abdomen, musculoskeletal and extremities, neurological, psychiatric and mental status.

Knee examinations will be done at Screening, Baseline, Week 2, Week 4, Week 8, Week 12, Week 18, and Week 24 (End of Study) or Early Termination. Knee examinations will be done for both knees at Screening and only for the Index Knee for subsequent visits. Knee examinations include range of motion, presence of an effusion (stroke test), crepitus on palpation with range of motion, stability of collateral ligaments, stability of cruciate ligaments, warmth on palpation of the joint, tenderness on palpation of the joint, gait, and skin appearance.

Both physical examination and knee examination parameters will be listed for each subject and summarized by frequency and percentage, as well as by shift from baseline.

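### SAP 4.4 bars early-exit data from summary tables, but SAP 3.8.4.2 to 3.8.4.4 tabulate the same safety data at an early-termination time point; both cannot be followed

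*SAP*

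**What the plan says.** Protocol 5.4 and 9.2.6 ask subjects who leave early to complete the Visit 9 assessments. Protocol 9.2.5.7 makes the early exit visit part of Visit 9, and unscheduled visits have their own section, 9.2.7.

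SAP 4.4 classes early exit as unscheduled: "data obtained from unscheduled assessments (which also includes early exit visits) will only be considered for baseline determination". It continues: "otherwise, unscheduled data will not be used in summary tables or included in the analyses". ACTH stimulation tests are the only exception in 4.4. SAP 3.1 repeats the rule for unscheduled data and adds an exception for deriving PK parameters.

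The safety sections say something else:

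- **Laboratory data in general (SAP 3.8.4.2):** "Clinical laboratory assessments will be summarized using standard summary statistics for continuous parameters".
- **HbA1c:** "HbA1c will be presented at Screening and at Week 24 (End of Study) or Early Termination visit".
- **Chemistry and hematology:** the list of time points ends "Week 4, Week 12 and Week 24 (End of Study) or Early Termination".
- **Serum cortisol:** the list ends "Week 12, Week 18, and Week 24 (End of Study) or Early Termination".
- **Weight (SAP 3.8.4.3):** "Weight will also be summarized per its collection schedule at Screening, Baseline, Week 12, and Week 24 (End of Study) or Early Termination". The vital-signs sentence ends with the same time point and also calls for a summary.
- **Examinations (SAP 3.8.4.4):** "Physical examinations will be presented at Screening, Baseline, Week 12, and Week 24 (End of Study) or Early Termination". Knee examinations carry the same final time point. Both types are to be listed, and also summarized by frequency and by shift from baseline.

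SAP 5, on deviations from the protocol, does not mention the matter.

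**The concern.** Two current SAP rules give opposite instructions for the same measurements. The baseline allowance in 4.4 does not help, because SAP 4.1 takes baseline before study drug, so a dosed leaver's exit value can never serve as one.

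If 4.4 governs, a leaver's last laboratory, cortisol, vital-sign, weight and examination values drop out of the safety tables, and so does the leaver's only post-dose HbA1c. That matters in a corticosteroid trial that admits subjects with non-insulin-dependent diabetes (Protocol 5.3) and lists blood-glucose effects among the known risks (Protocol 2.2). If 3.8.4 governs, the values appear, but one programmer could pool them with Week 24 and another could give them a separate row. The two sets of tables would differ, and the plan gives no basis for choosing between them.

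**Working it through.** **Comparing the rules by data type.** Post-dose time points are those named in SAP 3.8.4.2 to 3.8.4.4, leaving early termination aside.

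| Data | Post-dose time points tabulated | What a leaver loses if 4.4 governs |
|---|---|---|
| HbA1c | Week 24 only | every post-dose value |
| Weight, physical examination | Weeks 12 and 24 | every post-dose value, if exit is before the Week 12 visit |
| Chemistry, hematology | Weeks 1, 2, 4, 12 and 24 | everything after Week 4, if exit falls between the Week 4 and Week 12 visits |
| Cortisol, vital signs, knee examination | more visits, including Weeks 8 and 18 | the exit value only |

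**Inputs from the documents.** SAP 3.3: 120 per arm needed, 20% drop-out, 150 per arm randomized. Protocol 9.2.5: Week 4 visit on Day 29 ± 3, Week 12 visit on Day 85 ± 3, Week 24 on Day 169.

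**Assumptions, not in the documents.** Between 50% and 100% of leavers attend the exit visit. Exits are spread evenly over the 168 days from Day 2 to Day 169.

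1. The plan's own figure: 120 / (1 − 0.20) = 150 per arm, or 300 in total. This reproduces.
2. Leavers: 0.20 × 300 = 60; completers: 300 − 60 = 240.
3. Exit visits: 0.50 × 60 = 30 to 1.00 × 60 = 60, which is 10% to 20% of those randomized.
4. Subjects with a tabulated post-dose HbA1c: 240 under 4.4; 240 + 30 = 270 to 240 + 60 = 300 if exit values are shown.
5. Share of a pooled Week 24 row made up of exit values: 30/270 = 11.1% to 60/300 = 20.0%.
6. No tabulated post-dose weight or physical examination: the Week 12 window opens on Day 85 − 3 = Day 82, so exits on Days 2 to 81 count, which is 80 days. 80/168 = 0.476; 0.476 × 30 = 14.3 and 0.476 × 60 = 28.6, so about 14 to 29 subjects.
7. No tabulated chemistry or hematology after Week 4: the Week 4 window closes on Day 29 + 3 = Day 32, so exits on Days 33 to 81 count, which is 49 days. 49/168 = 0.292; 0.292 × 30 = 8.75 and 0.292 × 60 = 17.5, so about 9 to 18 subjects.

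**Sensitivity to drop-out.** With 5% drop-out there are 15 leavers and 285 completers; with 10%, 30 and 270. Steps 3 to 7 shrink accordingly.

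**The case against.** The best reply is that only the vital-signs and weight text says outright that data are summarized at early termination. Chemistry, hematology, HbA1c, cortisol and physical examinations are to be presented there, and 4.4 uses that same verb for listings. Knee examinations are merely said to be done at those times. On this view 3.8.4 echoes the protocol's label for Visit 9, 4.4 is the only text that says how exit data are handled, and so 4.4 governs.

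This does not remove the conflict. For vital signs and weight it is explicit. For laboratory data, the rule calling for summary statistics opens the section that holds the HbA1c, chemistry and cortisol time points. For examinations, the closing sentence asks for summaries as well as listings. Both rules are specific, one to the parameters and the other to the visit, and neither is given precedence.

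Some points do stand:

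- The counts depend on drop-out reaching the planning value and on two assumptions that the documents do not supply.
- Protocol 9.1.5.1 allows for a creatinine value from Visit 6 or Visit 8 in the imaging sub-study, so it would be too strong to say that no chemistry is drawn then. The SAP still does not tabulate chemistry at Weeks 8 or 18.
- Urinalysis is collected at early exit, but the SAP names no early-termination point for it. It lies outside the contradiction, though it could sensibly be treated the same way.
- A study-day window, as 4.4 uses for ACTH tests, or listings only would also be coherent if stated.
- The consequences are modest: exit values remain in listings, and clinically significant laboratory changes are recorded as adverse events (Protocol 10.2.7).

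**Conclusion.** The contradiction is real and should be resolved before the safety tables are programmed. Followed as written, 4.4 gives the worse result: at the planned drop-out, HbA1c after dosing would be summarized in completers only. The range of 30 to 60 affected exit visits, and the smaller counts for weight, physical examination, chemistry and hematology, hold only under the stated drop-out, attendance and even-spread assumptions. The existence of the conflict depends on none of them.

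The reach is limited. SAP 3.8.4 plans no safety hypothesis tests. Sample size is unaffected. No effect on efficacy is claimed: WOMAC data follow the study-day windows in SAP 4.1, and PtGA, MDGA and SF-36 are analysed at fixed planned weeks.

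**What to change.** 1. **SAP 4.4:** extend the ACTH exception to safety assessments made at the early exit visit: clinical chemistry, hematology, HbA1c, serum cortisol, vital signs, weight, and physical and knee examinations. Decide at the same time whether exit urinalysis should join them.
2. **SAP 3.1:** add the same exception to its list.
3. **SAP 3.8.4.2 to 3.8.4.4:** state that early termination is a separate row, with n and study day, and is not pooled with Week 24.
4. **Optional:** add to 4.4 a cross-reference saying that WOMAC data follow the windows in 4.1. The PtGA, MDGA and SF-36 analyses need no change.

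Removing the early-termination time point from 3.8.4 would also end the conflict, but would leave leavers' only post-dose HbA1c in listings alone.

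The cost is SAP wording and programming, with no new data or visits. The small downside is one extra row per safety table, holding values taken at varying study days.

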9.1.5.3 Knee Examination

At Visit 1a both knees will be examined. From Visit 2 onwards, only the Index knee will be examined.

The subject's knee will be examined for:

- Range of motion (0-45 degrees, 46-90 degrees, 91-135 degrees)
- Presence of an effusion (Stroke Test: zero, trace, 1+, 2+, 3+)
 - Zero: No wave produced on downstroke
 - Trace: Small wave on medial side with downstroke
 - 1+: Large bulge on medial side with downstroke
 - 2+: Effusion spontaneously returns to medial side after upstroke
 - 3+: So much fluid it is not possible to move the effusion out of the medial aspect of the knee
- Crepitus on palpation with range of motion (yes/no)
- Stability of collateral ligaments (stable, mild instability, moderate instability, unstable)
- Stability of cruciate ligaments (stable, mild instability, moderate instability, unstable)

- Warmth and tenderness on palpation of the joint (yes/no)
- Skin appearance (scars, redness, bruising, swelling; all as yes/no)
- Gait (normal, mild antalgia, moderate antalgia, severe antalgia)

If the examination reveals findings that indicate a possible infection in the Index knee (e.g., the knee is red and swollen with a moderate or large effusion, or is hot and swollen with a moderate or large effusion), a blood sample will be collected for hematology testing and the subject should be referred for further specialist assessment as soon as possible. If an Index knee joint infection is suspected, this should be reported as an SAE (see Section 10.1.4 for details), and every effort should be made to retrieve documentation of the diagnosis and diagnostic procedures performed. If an Index knee finding appears to meet the criteria for further investigation and/or review by the SRC, contact the Medical Monitor (see Sections 4.3 and 4.4 for details).

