9.2.7 Unscheduled Visits

Unscheduled visits may be performed at the Investigator's discretion if there are safety findings of concern at scheduled visit assessments or reported by subjects between visits.

An unscheduled visit should also be performed in the following circumstances:

- **All subjects** - If the subject requires additional rescue medication between scheduled visits, they may call the site to obtain an additional bottle of rescue medication.
- **All subjects** - If at any time during the study a subject independently reports symptoms indicative of an infection in the Index knee (e.g., a red and swollen knee with moderate or large effusion, or a hot and swollen knee with a moderate or large effusion), a blood sample will be collected for hematology testing and the subject should be referred for further specialist assessment as soon as possible.
- **Subjects with abnormal ACTH stimulation test results** - If the ACTH stimulation test performed at Visit 9 (Week 24/End-of-Study/Early Exit) is abnormal (as per the unblinded Medical Monitor's assessment), the subject should be asked to return to the site for a repeat test to confirm the initial result and additional safety evaluations, as required.
- **Subjects with abnormal serum cortisol test results** – If the serum cortisol test at Visit 9 (Week 24/End-of-Study/Early Exit) is abnormal as per the unblinded Medical Monitor's assessment (and the subject did not already complete an ACTH stimulation test at that visit), the subject should be asked to return to the site to complete an ACTH stimulation test.
- **Subjects who withdraw early** – If a subject withdraws early from the study and their most recent visit serum cortisol was <350 nmol/L (<12.7 µg/dL) (as per the unblinded Medical Monitor's review) the subject should be asked to return to the site for an ACTH stimulation test and additional safety evaluations, as required.

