10.2.5 Symptoms and Signs of Adrenal Insufficiency

Subjects will be closely monitored for clinical signs and symptoms of AI. These can include:

- Extreme fatigue or weakness.
- Weight loss and decreased appetite.
- Nausea, diarrhea or vomiting.
- Low blood pressure, dizziness, or syncope.
- Abdominal pain.
- Unusual muscle or joint pain.
- Unusual changes in thinking, including irritability, confusion.
- Depression (or depressive symptoms).
- Electrolyte abnormalities e.g.,
 - Sodium <133 mEq/L (<133 mmol/L).
 - Potassium >5.5 mEq/L (>5.5 mmol/L).

Monitoring of clinical signs and symptoms will be performed by the Investigator. In addition, the Medical Monitor will review safety data (which also includes morning serum cortisol values and cortisol values following ACTH stimulation).

If AI is suspected, a cortisol sample should be collected and a subsequent ACTH stimulation test performed if indicated.

If AI is confirmed the Investigator may consider prescribing glucocorticoid replacement therapy if warranted. Subjects with confirmed AI should be referred to an Endocrinologist (or other appropriate specialist) for management until resolution of AI. If the Subject's AI is ongoing at their final scheduled study visit, the Investigator should follow up with the subject approximately 3 months later, with at least 1 additional contact within that 3-month period.

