### 3. STATISTICAL METHODOLOGY

#### 3.1 General Principles

All collected study data will be presented in listings. All derivations and statistical analyses will be performed using SAS® software Version 9.4 (or higher) or Phoenix® WinNonlin® Version 8.3 (or higher) (Certara USA, Inc., Princeton, NJ). Prior and concomitant medications/procedures will be coded using World Health Organization (WHO) Drug Dictionary Enhanced March 1, 2021 (or most recent version prior to data base lock). Adverse events will be coded using Medical Dictionary for Regulatory Activities (MedDRA) Version 24.0 (or most recent version prior to data base lock).

Unless stated otherwise, descriptive summaries for continuous variables will include n (number of subjects with non-missing results), mean, standard deviation (SD), median,  $Q_1$ ,  $Q_3$ , minimum, and maximum. For categorical variables, n and percent will be provided. Percentages will be calculated out of the number of subjects in the given sample with a non-missing result.

The primary means of efficacy data collection will be via an electronic patient-reported outcome (ePRO) device. Subjects will be provided with a hand-held device programmed to prompt the subject to record data as required throughout the study. The primary means of non-efficacy data collection will be via the electronic case report forms (eCRFs).

Summaries presented by collection day and/or by time point will be based on scheduled assessments as planned in the protocol except for all WOMAC data (See Section 4.1). Unscheduled assessments will be presented in listings and will not be included in the analyses except for: determination of baseline as described in Section 4.3, ACTH stimulation test summaries (See Section 4.4), and for the derivation of PK parameters.

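### Under SAP 4.4, hematology, chemistry, cortisol and knee findings from symptom-driven unscheduled assessments appear in listings only, and no by-arm worst post-dose summary makes up for it

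*SAP*

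**What the plan says.** SAP 4.4 sets the rule: "Except for ACTH stimulation test results as described below, data obtained from unscheduled assessments (which also includes early exit visits) will only be considered" for setting baseline, and "otherwise, unscheduled data will not be used in summary tables or included in the analyses". It adds: "All unscheduled data will be presented in the listings". SAP 3.1 states the same rule, with exceptions for baseline, "ACTH stimulation test summaries (See Section 4.4), and for the derivation of PK parameters".

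ACTH results are handled differently. SAP 4.4 maps them, unscheduled ones included, to visit windows: "When more than one result for a subject occurs within one visit window, the worst result (i.e., Fail) will be mapped to that visit".

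The protocol uses extra assessments to follow up safety signals. Section 9.2.7 allows an unscheduled visit at the Investigator's discretion "if there are safety findings of concern at scheduled visit assessments or reported by subjects between visits". For findings that suggest index-knee infection, sections 9.1.5.3 and 9.2.7 both say that "a blood sample will be collected for hematology testing and the subject should be referred for further specialist assessment as soon as possible". Section 10.2.5 says: "If AI is suspected, a cortisol sample should be collected and a subsequent ACTH stimulation test performed if indicated".

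**The concern.** An unscheduled safety result usually exists because someone was worried. Adrenal suppression and local knee reaction are the two risks that Protocol 2.2 singles out for close monitoring, and redness, warmth, swelling and 2+ effusion are components of the stopping rule in Protocol 4.4. The SAP compares the arms on planned-visit values and leaves the signal-driven values to listings, which give no comparison by arm. A subject may have recovered by the next planned visit, and the by-visit table then shows only the recovered value.

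**Working it through.** The plan gives no figure on this point. The check sets the rules side by side and takes day differences from the protocol's visit days.

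**Step 1. Where each off-schedule result goes.**

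| Result | Source in the protocol | Exempt in SAP 4.4? | By-arm table reached |
|---|---|---|---|
| ACTH stimulation test | 9.1.5.1.2, 9.2.7 | Yes | Percent positive, worst result per window |
| Hematology | 9.2.7, suspected knee infection | No | None |
| Serum cortisol | 10.2.5, suspected adrenal insufficiency (no timing given) | No | None |
| Chemistry | Discretionary; low sodium and high potassium are listed signs in 10.2.5 | No | None |
| Knee examination | Discretionary; no section requires one at an unscheduled visit | No | None |

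The ACTH windows end on Days 9, 22, 43, 71, 106 and 148, and the next ones begin on Days 10, 23, 44, 72, 107 and 149. They leave no gap, so no post-dose ACTH result is lost.

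**Step 2. Whether another table fills the gap.** SAP 3.8.4.2 summarizes laboratory values by planned time point and puts high/low flags in listings. SAP 3.8.4.4 tabulates knee findings at named visits, with shifts from baseline. The minimum and maximum required by SAP 3.1 are computed on scheduled data. No worst post-dose or any-time abnormality table is planned.

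**Step 3. How long the scheduled data are silent.** Nominal days come from Protocol 9.2.4 and 9.2.5. Dosing is on Day 1, so follow-up to Day 169 spans 168 days.

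- Hematology and chemistry, Days 1, 3, 15, 29, 85, 169: gaps of 2, 12, 14, 56 and 84 days. The last two make up 56 + 84 = 140 of 168 days, or 83%. With visit windows of ±3 days (Visits 5 and 7) and ±7 days (Visit 9), they can run 50 to 62 and 74 to 94 days.
- Knee examination, Days 1, 15, 29, 57, 85, 127, 169: gaps of 14, 14, 28, 28, 42 and 42 days. Visit 3 (Day 3) is for blood samples and AE recording only (Protocol 9.2.5.1).
- Cortisol, Days 1, 3, 15, 29, 57, 85, 127, 169: gaps of 2, 12, 14, 28, 28, 42 and 42 days.

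One caveat: the eGFR paragraph in Protocol 9.1.5.1 mentions creatinine values from Visits 6 and 8. The lists for those visits (9.2.5.4, 9.2.5.6) include only cortisol and PK samples, and SAP 3.8.4.2 shows no chemistry at Weeks 8 or 18. The gaps above follow the visit lists.

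**Step 4. What the AE tables carry.** Suspected index-knee infection must be recorded as an SAE (Protocol 10.1.4), so it reaches the serious TEAE table in SAP 3.8.4.1. That table shows coded terms, not white-cell counts or effusion grades. Protocol 10.3.1 prefers a diagnosis to an abnormal laboratory value. After randomization, cortisol results go to the Medical Monitor and not to the site (Protocol 6.2, 9.1.5.1.1), so an Investigator would not routinely be able to record a low value as an AE.

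**Step 5. Early exit.** SAP 4.4 classes early-exit visits as unscheduled and excludes them. SAP 3.8.4.2 to 3.8.4.4 present early-termination values alongside Week 24. Both cannot apply. At the planned 20% drop-out, at most 0.20 × 300 = 60 subjects (about 30 per arm) are affected; fewer if some do not attend an exit visit.

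**The case against.** The strongest reply is that the harms themselves do reach by-arm tables. Suspected knee infection is an SAE, clinically significant laboratory changes count as AEs (Protocol 10.2.7), and unscheduled ACTH tests, the main adrenal work-up in Protocol 9.2.7, are tabulated on a worst-result basis. Cortisol is summarized at every post-dose visit and plotted. The rule is pre-specified, nothing is hidden from the listings, and safety has no hypothesis tests. All of this stands, and it limits the point to measured values and grades.

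It does not remove the point. The ACTH table gives only a positive count and percentage. When cortisol is at or below 138 nmol/L with symptoms, Protocol 9.1.5.1.2 places the ACTH test at the next scheduled visit, which may be weeks after the cortisol sample. The SAP also gives no reason for applying a worst-result rule to ACTH tests and not to the other results.

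A reader might infer more than the documents support:

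- That no unscheduled result reaches any summary table. The ACTH exemption contradicts this.
- That the worst cortisol or hematology value never reaches a by-arm table. It may fall at a scheduled visit, where the minimum and maximum would show it.
- That the Phase 1 cortisol falls would have been missed here. Protocol 1.2.2 places the noticeable decrease at 48 hours and says that the two falls of more than 75% had recovered by one and three weeks. Visit 3 samples at about 48 hours, so those falls show quick recovery but not that this schedule would miss them.

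**Conclusion.** The point holds in limited form, as a change that should be made. A stated rule, not an omitted detail, keeps signal-driven hematology, chemistry, cortisol and knee-examination results out of the comparison by arm, and no other table restores them. It matters most for hematology and chemistry, with 140 of 168 follow-up days inside two long gaps, and for knee reactions before the Week 2 examination. It matters less for cortisol, which is scheduled at every post-dose visit.

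It is tempting to conclude that the safety comparison is biased towards no difference. That is possible but not shown: it would need such visits to cluster in one arm, and the documents give neither their number nor their split. The conclusion assumes that sites follow the nominal visit lists and that some subjects are sampled or examined off schedule. The efficacy analyses do not depend on it.

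**What to change.** Keep all by-visit safety tables on scheduled data. Amend SAP 3.1 and 4.4 to add one by-arm summary of the worst post-dose result, scheduled plus unscheduled, covering:

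- index-knee effusion grade, warmth, redness and swelling;
- leukocytes and neutrophils;
- sodium and potassium;
- serum cortisol.

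State for each item which direction counts as worst. Flag cortisol samples taken outside the 7 to 11 a.m. window that Protocol 9.1.5.1.1 requires. Show the number of subjects with unscheduled samples in each arm, because a worst-value summary depends on how often subjects are sampled and can itself mislead if that differs between arms.

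In the same edit, reconcile the early-exit exclusion in SAP 4.4 with the early-termination summaries in SAP 3.8.4.2 to 3.8.4.4, and align the exceptions listed in 3.1 and 4.4 (PK derivation appears only in 3.1).

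The cost is SAP wording and one added table. It needs no new data and leaves clinical procedures unchanged. If the amendment comes after unblinding, label the table as an addition.
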